## **12.2 Populations for Analysis**

The Full Analysis Set (FAS) will serve as the primary population for the analysis of tumor response and other efficacy-related data. The FAS is a subset of all enrolled patients, with patients excluded for the following reasons:

- Failure to receive at least one dose of entinostat and pembrolizumab
- Lack of baseline data for those analyses that require baseline data

A supportive analysis using the Per-Protocol (PP) set may be performed by excluding patients with important deviations from the protocol that may substantially affect the results of the primary efficacy analyses. The final determination on protocol violations, and thereby the composition of the PP set, will be made prior to locking the clinical database and final analysis and will be documented in a separate memo.

The safety population will be used for the analysis of safety data in this study. The safety population will consist of all patients who receive at least one dose of entinostat and pembrolizumab. At least one laboratory or other safety-related assessment subsequent to at least one dose of entinostat and pembrolizumab is required for inclusion in the analysis of a specific safety parameter. To assess change from baseline, a baseline measurement is also required.

A patient that experiences an adverse event meeting DLT criteria during C1 or who receives the full dose of pembrolizumab and all doses of entinostat during C1 without experiencing a DLT, is considered a DLT-evaluable patient.

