3.2.4 Safety Analysis Set

Without otherwise specified, the Safety Analysis Set will be used for the analysis of safety data in both the Phase 1b and Phase 2 portions of the study. The Safety Analysis Set will include all patients who received at least one dose of either study drug, entinostat, or pembrolizumab. At least one laboratory or vital sign measurement obtained, subsequent to at least one dose of study treatment, is required for inclusion in the analysis of a safety specific parameter. To assess change from baseline, a baseline measurement is also required.

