3.10 Safety Analysis

Safety analyses will be performed on the Safety Analysis Set.

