3.10.1 Adverse Events

An AE is defined as any untoward medical occurrence in a patient or clinical

investigation patient administered a pharmaceutical product, and that does not necessarily have a causal relationship with this treatment. An AE can therefore be any unfavorable and unintended sign (including an abnormal laboratory finding), symptom, or disease, temporally associated with the use of a medicinal (investigational) product, whether or not the AE is related to the medicinal (investigational) product. The term also covers laboratory findings or results of other diagnostic procedures that are considered to be clinically relevant as determined by the Investigator.

Analyses of AEs will be based on the principle of treatment emergence. Treatment-emergent AEs are defined as having onset after study drug dosing or a sign, symptom, or diagnosis that worsens after study drug dosing. Henceforth, whenever an analysis or summary of AEs is mentioned, it is intended that this is in reference to TEAEs, unless it is stated otherwise.

If AE start dates are completely missing or partially missing, the date imputation rules described previously in Section 3.1.4 will be applied for the determination of treatment-emergence. This algorithm will be used only if the end date of the AE (if reported) indicates the event was not resolved before the first administration of study drug. Imputed AE dates will not be used to calculate the duration of AE episodes.

All AEs will be coded according to System Organ Class (SOC) and Preferred Term (PT) using the Medical Dictionary for Regulatory Activities (MedDRA) dictionary (Version 18.0 or later).

For the escalation phase, the observed DLT rate in each dose cohort will be calculated by the crude proportion of patients who experienced DLT with a 2-sided, 95% exact binomial CI.

For Phase 1, AE relatedness criteria is defined as “definitely not related”, “probably not related”, “probably related” and “definitely related”.

A summary of AEs, including incidences of:

- AEs
- SAEs
- AEs related to entinostat (“not related”, “unlikely related”, “possibly related”

or “related” for Phase 2)

- AEs related to pembrolizumab (“not related”, “unlikely related”, “possibly related” or “related” for Phase 2)
- AEs related to any study drug
- SAEs related to entinostat, pembrolizumab, or both
- AEs leading to dose modification of entinostat, pembrolizumab, or both
- AEs leading to discontinuation of entinostat, pembrolizumab, or both

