Table 14.3.5C	PFS by baseline LDH (%>ULN) (irRECIST) – Phase 2 (FAS)
Table 14.3.5D	PFS by previously treated with ipilimumab and PD-1 (Melanoma cohort only) (irRECIST) – Phase 2 (FAS)
Table 14.3.5E	PFS by Previously treated with BRAF/MEK inhibitor (Melanoma cohort only) (irRECIST) – Phase 2 (FAS)
Table 14.3.5F	PFS by baseline non-classical monocytes (cut-off median for NSCLC, but it might change for other cohorts) (irRECIST) – Phase 2 (FAS)
Table 14.3.5G	PFS by NLR (irRECIST) – Phase 2 (FAS)
Table 14.3.5H	PFS by dNLR (irRECIST) – Phase 2 (FAS)
Table 14.3.5I	PFS by smoking status (current smoker, former smoker, never a smoker) (NSCLC cohorts only) (irRECIST) – Phase 2 (FAS)
Table 14.3.6	Clinical Benefit Rate (irRECIST) – Phase 2 (FAS) (RECIST 1.1) – Phase 2 (FAS)
Table 14.3.7A	PFS status at 6 months (irRECIST) - Phase 2 (FAS)

Table 14.3.7B	PFS status at 6 months – (RECIST 1.1) – Phase 2 (FAS)
Table 14.3.8A	PFS (irRECIST) - Phase 2 (FAS)
Table 14.3.8B	PFS (RECIST 1.1) – Phase 2 (FAS)
Table 14.3.9	Overall Survival – Phase 2 (FAS)
Table 14.3.10	Time to Response – Phase 2 (FAS)
Table 14.3.11	Duration of Response – Phase 2 (FAS)
Table 14.4.1	Overall Treatment-Emergent Adverse Event Information - Phase 2 (Safety)
Table 14.4.1.1	Dose Limiting Toxicities – Phase 1b (Safety)
Table 14.4.1.2	Treatment-Emergent Adverse Events by System Organ Class and Preferred Term -Phase 1b (Safety)
Table 14.4.2	Treatment-Emergent Adverse Events by System Organ Class and Preferred Term - Phase 2 (Safety)
Table 14.4.3	Treatment-Emergent Adverse Events by Preferred Term and Maximum Severity – Phase 2 (Safety)
Table 14.4.4.1	Treatment-Emergent Adverse Events by Preferred Term and Relationship to Any Study Drug – Phase 1b (Safety)
Table 14.4.4.2	Treatment-Emergent Adverse Events by Preferred Term and Relationship to Any Study Drug – Phase 2 (Safety)
Table 14.4.4.3	Treatment-Emergent Adverse Events by Preferred Term and Relationship to Entinostat Alone – Phase 2 (Safety)

Table 14.4.4.4	Treatment-Emergent Adverse Events by Preferred Term and Relationship to Pembrolizumab Alone – Phase 2 (Safety)
Table 14.4.5.1	Treatment-Emergent Adverse Events with Severity of Grade 3 or Greater – Phase 2 (Safety)
Table 14.4.5.2A	Treatment-Emergent Adverse Events with Severity of Grade 3 or Greater and Judged Related to Any Study Drug – Phase 2 (Safety)
Table 14.4.5.2B	Treatment-Emergent Adverse Events with Severity of Grade 3 or Greater and Judged Related to Any Study Drug – Phase 1b

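### No planned analysis uses the protocol's DLT-evaluable definition: the Phase 1b DLT rate is put on the Safety Analysis Set, where a dosed but non-evaluable patient can only lower it

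*SAP*

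**What the plan says.** **Protocol, the evaluable patient.** Section 12.2, among the populations for analysis, describes two routes to being DLT-evaluable: "A patient that experiences an adverse event meeting DLT criteria during C1 or who receives the full dose of pembrolizumab and all doses of entinostat" without a DLT in that cycle. Section 8.2.1.2 gives the same definition.

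**Protocol, the reporting set.** Section 12.2 also defines the safety population: "The safety population will consist of all patients who receive at least one dose of entinostat and pembrolizumab". Section 12.4.7 makes that population the default for safety analyses and includes DLTs in its list of summaries. The synopsis, under Safety Analyses, does the same. Neither names the DLT-evaluable patients as the denominator of the DLT rate.

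**SAP.** Section 3.2 defines Full, Per-Protocol, Evaluable (an efficacy set tied to the Week 6 scan), Safety and Pharmacokinetic sets. There is no DLT-evaluable set; the term appears only in the amendment history in SAP 1. Section 3.2.4 is broader than the protocol's safety population: "The Safety Analysis Set will include all patients who received at least one dose of either study drug, entinostat, or pembrolizumab". Section 3.10 states: "Safety analyses will be performed on the Safety Analysis Set". Section 3.10.1 gives the estimator: "the observed DLT rate in each dose cohort will be calculated by the crude proportion of patients who experienced DLT", with a two-sided 95% exact binomial interval and no stated denominator. The list of tables in 6.1 has one DLT table, 14.4.1.1: "Dose Limiting Toxicities – Phase 1b (Safety".

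**How the rate is used.** Protocol 8.2.1.3 defines the MTD as the highest dose level with fewer than 33% of patients having a DLT in Cycle 1 (C1). Protocol 8.2.1.1 writes the escalation rule as a percentage and as a count: fewer than 2 of up to 6 allows escalation, and 2 or more marks the DLT dose level.

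**The concern.** A DLT rate is meant to describe patients who were observed, at the planned exposure, through the whole DLT window. A patient who stops early or misses doses without a DLT has not shown that the dose is tolerated, yet the Safety set counts that patient as a full DLT-free observation.

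Such patients are foreseeable under the protocol's own rules.

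- Sections 8.2.1.1 and 10 allow replacement of patients who leave before completing C1 for reasons other than drug-related toxicity. If already dosed, they stay in the Safety set beside their replacements.
- Table 8-2 allows entinostat to be interrupted for a toxicity of Grade 2 or lower and resumed at the original dose. One C1 dose missed for that reason meets none of the DLT criteria in 8.2.1.2, yet the patient has not received all doses and so is not evaluable.
- On days when both drugs are given, entinostat is taken first. A patient who takes it and never receives the infusion is in the SAP's Safety set, though not in the protocol's safety population.

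Determining the DLTs and the MTD or recommended Phase 2 dose is the Phase 1b primary objective. With 3 to 6 patients per dose level, one patient moves the reported rate by several percentage points, and the report can show a rate that does not match the basis on which the dose level was judged.

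**Working it through.** **1. The plan's own figures.** Protocol 12.1.1 (and SAP 2.3.1) states a 3% chance of halting escalation at a true DLT rate of 5% or less, and 83% at 50%. Under a 3+3 rule with halting at 2 or more DLTs:

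P(halt) = P(2 or more of 3) + P(exactly 1 of 3) × P(1 or more of the next 3)

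- p = 0.05: 0.00725 + 0.135375 × 0.142625 = 0.0266, stated as 3%.
- p = 0.50: 0.5 + 0.375 × 0.875 = 0.828, stated as 83%.

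Both are reproduced. A fixed 6 patients gives 3.3% and 89.1%, and a fixed 3 gives 0.7% and 50.0%; neither matches both stated figures. The calculation treats each enrolled patient as a complete DLT observation. It makes no allowance for non-evaluable patients.

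**2. Direction of the effect.** Let x be the number of patients with a DLT, e the number evaluable, and m the number dosed but not evaluable. Anyone with a DLT in C1 is evaluable by definition, so the m patients contribute nothing to x. The evaluable rate is x/e and the Safety-set rate is x/(e + m). Hence x/(e + m) ≤ x/e, with equality only if m = 0 or x = 0.

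**3. Size.** The documents do not give m. As an assumption, take m = 0, 1 or 2 at one dose level. The exact (Clopper-Pearson) limits are the 0.025 quantile of Beta(x, n − x + 1) and the 0.975 quantile of Beta(x + 1, n − x).

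| Non-evaluable patients (m) | 2 DLTs, 6 evaluable | Exact 95% CI | Against <33% |
|---|---|---|---|
| 0 | 2/6 = 33.3% | 4.3-77.7% | not met |
| 1 | 2/7 = 28.6% | 3.7-71.0% | met |
| 2 | 2/8 = 25.0% | 3.2-65.1% | met |

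Two other cases:

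- 1 DLT: 1/6 = 16.7%, 1/7 = 14.3%, 1/8 = 12.5%. All are below 33%, so the reading does not change.
- 6 escalation plus 9 confirmation patients at one dose, 15 evaluable, 5 DLTs: 5/15 = 33.3%, 5/16 = 31.3%, 5/17 = 29.4%. The pattern at the boundary is the same, with smaller steps.

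**4. What does not move.** In the first case the number of DLTs is 2 in every row. Under the count form of the escalation rule the dose level has been reached whatever the table's denominator.

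**The case against.** **The SAP follows the protocol.** A reader might infer that the SAP departs from a protocol that requires the evaluable denominator. The documents do not support that. The synopsis and Protocol 12.4.7 put DLT reporting on the safety population by default, and 12.2 defines the evaluable patient without attaching the DLT rate to it. The gap starts in the protocol and the SAP carries it forward, so both need the edit.

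**The dose decision does not depend on this table.** A reader might infer that the choice of set could change escalation or the recommended dose. The operating rule is a count, applied during the study by the sponsor's physicians with the investigators, and the recommended dose also weighs cumulative toxicity, delays, reductions and feasibility. This stands. What remains exposed is the reported rate, its interval and their agreement with the percentage wording of the MTD definition.

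**The DLT rate is not a primary endpoint.** Determining DLTs and the MTD is the primary objective, but SAP 2.2.2 lists it among the safety items under secondary endpoints. No test is attached, and the rate is a descriptive proportion. This also stands.

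**Dilution may be small or absent.** An event at least possibly related to entinostat that requires a dose reduction, discontinuation or more than 2 held doses is itself a DLT, so it counts in both numerator and denominator. The patients at issue are mainly non-toxicity dropouts and those with a short hold or missed dose. If there are none, the two rates are identical. The intervals in the table also overlap heavily. All of this limits the size of the effect; it does not change its direction.

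**Part of the evidence is a table title.** SAP 3.10.1 names no denominator, and 3.2.4 leaves room for exceptions to the Safety set. But no exception is stated, 3.10 applies the Safety set to the section, and no other DLT table is listed.

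**Conclusion.** The point holds as a reporting defect shared by both documents. The protocol defines who is evaluable for DLT, no planned analysis uses the definition, and the stated set gives a DLT rate that can only be equal to or below the rate in evaluable patients, with the exact interval shifted accordingly. At 2 DLTs among 6 evaluable patients, one extra non-evaluable patient lowers the reported rate by 33.3 − 28.6 = 4.7 percentage points and two lower it by 33.3 − 25.0 = 8.3, in each case from at the 33% limit to below it.

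These sizes rest on an assumed 0 to 2 non-evaluable patients at a dose level and on a result at the boundary. With no such patients, or with no DLTs, nothing changes. The documents do not show that dilution has occurred, and they do not support a claim that escalation or dose selection would differ.

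**What to change.** - In SAP 3.2, add a DLT-evaluable set with the definition already in Protocol 12.2.
- In SAP 3.10.1, name it as the denominator of the DLT rate and exact interval, and relabel Table 14.4.1.1 to match.
- List dosed Phase 1b patients who are not evaluable, with reasons, and keep the Safety-set version as supportive.
- In Protocol 12.4.7 and the synopsis, record the DLT rate as the exception to the safety-population default.
- While editing the table, state which dose levels it covers. SAP 3.1.1 tabulates the dose determination phase by the 3 mg cohort and moves 5 mg patients to the expansion phase, whereas 3.10.1 speaks of each dose cohort.

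The cost is one set definition, one table title, a listing and a sentence in each protocol location. No new data collection should be needed, since dosing and DLTs are already recorded. The statistical price is a slightly smaller denominator and a slightly wider interval whenever non-evaluable patients exist.

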6.2 List of Figures

Figure 14.3.1.1	Swimmer Lane Plot (NSCLC) – Cohort 1
Figure 14.3.1.2	Swimmer Lane Plot (NSCLC) – Cohort 2
Figure 14.3.1.3	Swimmer Lane Plot (Melanoma) – Cohort 3
Figure 14.3.1.4	Swimmer Lane Plot (Colo-rectal) - Cohort 4
Figure 14.3.2.1-4	Waterfall Plots (Cohort 1-4)
Figure 14.3.3.1-4	Spider Lane Plots (Cohort 1-4)
Figure 14.3.4.1	Prior Therapy Swimmer Lane Plot for CR/PR Patients (Cohort 2)

Figure 14.3.4.2	Prior Therapy Swimmer Lane Plot for CR/PR Patients (Cohort 3)

6.3 List of Listings

Number	Title
Listing 16.2.1.1	Study Enrollment and Analysis Populations
Listing 16.2.1.2	Patients Not Evaluable for Efficacy or Safety Analysis
Listing 16.2.2.2	Study Disposition
Listing 16.2.2.3	Post-Treatment Follow-up
Listing 16.2.2.4	Post-Treatment Anti-Cancer Therapy
Listing 16.2.3.1	Exceptions to Protocol Eligibility Criteria
Listing 16.2.4.1	Demographic Characteristics
Listing 16.2.1.6	Cancer History (All cohorts)
Listing 16.2.1.7	Prior Systemic Anti-Cancer Therapy
Listing 16.2.1.8	Prior Surgery
Listing 16.2.1.9	Prior Radiation Therapy
Listing 16.2.1.10	Medical History
Listing 16.2.1.11	Entinostat Administration

Listing 16.2.1.12	Pembrolizumab Administration
Listing 16.2.1.13	Concomitant Medications
Listing 16.2.1.14	Concomitant Procedures
Listing 16.2.1.15	Protocol Deviations
Listing 16.2.2.1	PK Plasma Concentrations for Entinostat
Listing 16.2.2.2	PK Plasma Concentrations for Pembrolizumab
Listing 16.2.2.3	PK Parameters for Entinostat
Listing 16.2.2.4	PK Parameters for Pembrolizumab
Listing 16.2.3.1	Adverse Events
Listing 16.2.3.2	Serious Adverse Events
Listing 16.2.3.3	Adverse Events with Action Taken of Dose of Either Drug Reduced, Held, or Discontinued Permanently
Listing 16.2.3.4	Deaths and Overall Survival
Listing 16.2.3.5	Clinical Laboratory Values – Hematology, WBC Count and Differential
Listing 16.2.3.6	Clinical Laboratory Values – Hematology, Erythrocytes and Platelets
Listing 16.2.3.7	Clinical Laboratory Values – Chemistry, Renal
Listing 16.2.3.8	Clinical Laboratory Values – Chemistry, Hepatic
Listing 16.2.3.9	Clinical Laboratory Values – Chemistry, Electrolytes

Listing 16.2.3.10	Clinical Laboratory Values – Metabolic
Listing 16.2.3.11	Patients with Laboratory Values Out of Normal Range with CTCAE Toxicity Grade
Listing 16.2.3.12	Vital Signs
Listing 16.2.3.13	12-Lead Electrocardiograms
Listing 16.2.3.14	ECOG Performance Status
Listing 16.2.3.15	Clinical Disease Assessments
Listing 16.2.4.1	Imaging
Listing 16.2.4.2	Target Lesions
Listing 16.2.4.3	Non-Target Lesions
Listing 16.2.4.4	New Lesions
Listing 16.2.4.5	RECIST 1.1 Response
Listing 16.2.4.6	irRECIST Response
